1.1 Objectives and Endpoints

Estimands for the co-primary and secondary endpoints are defined as follows:

- Population: Primary Analysis Set (PAS) and specified sub-population (Section 4)
- Intercurrent-event strategies (IES):
 - o For binary endpoints, a hybrid estimand strategy is used. For ICEs of study treatment discontinuation for reasons other than commercial availability and extraordinary circumstances including study treatment supply issues and site termination, the composite strategy will be used where participants with these ICEs are classified as non-responders subsequent to discontinuation. To handle the ICE of study treatment discontinuation due to commercial availability and extraordinary circumstances including study treatment supply issues and site termination, the hypothetical scenario where these patients remained on study treatment is envisaged as the target of estimation (see details on imputation in Section 5.1.5).
 - o For continuous endpoints a hybrid estimand strategy is used. For ICEs of study intervention discontinuation for reasons other than commercial availability and extraordinary circumstances including study treatment supply issues and site termination, the composite strategy will be used such that measurements after the ICEs will return to baseline. To handle the ICE of study treatment discontinuation due to commercial availability and extraordinary circumstances including study treatment supply issues and site termination, a hypothetical scenario is envisaged in which these patients remained for the rest of the study and measurements after this ICE will be imputed (see details imputation in Section 5.1.5).
- Population level summary (PLS):

[figure not shown]
o Binary endpoints: proportions

o Continuous endpoints: LS mean

Objectives and Endpoints

Objectives	Endpoints
Primary	
CCI	
To assess the effect of mirikizumab on clinical remission by CDAI and endoscopic response a	Proportion of participants achieving clinical remission by CDAI (CC) at Week 52 of AMAX

Objectives	Endpoints
	Proportion of participants achieving endoscopic response (defined by CC) in SES-CD Total Score) at Week 52 of AMAX
Secondary	

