5.1.5 Missing Data Imputation

Intercurrent events (FDA 2017) are events which occur after the study intervention initiation and make it impossible to measure a variable or influence how it should be interpreted. Section 1.1 includes intercurrent events for the primary and secondary endpoints. The missing data methods described below may be used to address the intercurrent event strategies proposed for this study.

Non-Responder Imputation

A hybrid estimand strategy will be used to handle binary endpoints:

- Patients who discontinue study treatment due to reasons other than commercial availability and extraordinary circumstances including study treatment supply issues and the site termination, are categorized as treatment failures after discontinuation. As such, these patients are not considered missing from the perspective of the estimand of interest.
- The hypothetical strategy will be used to handle the ICE of study treatment discontinuation due to commercial availability and extraordinary circumstances including study treatment supply issues and the site termination. Participants with the ICE will be excluded from analysis for timepoints of interest after the ICE. The assumption behind this approach is that measurements after this ICE are missing completely at random and thus the estimation can be implemented using observed values.

^a Unless otherwise specified, these treatment arms are not included in the modeling to estimate treatment effect for MMRM and ANCOVA analysis. Also these treatment arms may be excluded from some tables or figures to simplify the output.

A small number of patients who completed study treatment up to the time point of interest but are sporadically missing the binary endpoint data will still require imputation. These patients will be imputed using NRI.

Modified Baseline Observation Carried Forward (mBOCF)

As a primary analysis for continuous variables, the ANCOVA with mBOCF approach will be used for handling missing data. For continuous endpoints a hybrid estimand strategy is used:

- For ICEs of study intervention discontinuation due to reasons other than commercial
 availability and extraordinary circumstances including study treatment supply issues and
 the site termination, the composite strategy will be used such that measurements after the
 ICEs will return to baseline. As such, these patients are not considered missing from the
 perspective of the estimand of interest.

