For the co-primary endpoints and selected secondary endpoints, missing data will be imputed using hybrid multiple imputation as a sensitivity analysis. Missing data for reasons of treatment discontinuation due to commercial availability and extraordinary circumstances including study treatment supply issues and the site termination will be imputed by multiple imputation (MI), while missing data due to treatment discontinuation for reasons other than commercial availability and extraordinary circumstances including study treatment supply issues and the site termination will be categorized as non-responders. Sporadically missing data (i.e., when a patient was still in the treatment period but data was not collected) will be imputed by MI.

As Observed Analysis

For some endpoints, patients who are missing the endpoint data for a specific visit for any reason including intercurrent events will be excluded from the analysis for that visit. Simple descriptive summaries will be presented.

[figure not shown]

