5.3.3 Supplemental Analysis

In addition to the NRI imputation method, an analysis in the PAS population using mNRI and observed case will also be presented as further analyses (see Section 5.1.5) for binary endpoints. The co-primary endpoints will also be analyzed in the mITT population. Additional details are described in Appendix 2 in Section 6.2.

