5.4.1.3 Sensitivity Analysis

Refer to Section 5.3.3 for details regarding the methods used for sensitivity analyses that may be used for binary secondary endpoints. Additional details are described in Appendix 2 Section 6.2.

For continuous endpoints, MMRM will be used as sensitivity analysis (see Section 5.1.5).

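### The main NRI and mBOCF rules keep other-reason stops as failures but drop commercial-availability and supply stops, so at late visits they do not estimate the SAP 1.1 target

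*SAP*

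**What the plan says.** SAP 1.1 sets a hybrid estimand. For binary endpoints, when treatment stops because of commercial availability or extraordinary circumstances, "the hypothetical scenario where these patients remained on study treatment is envisaged as the target of estimation". For continuous endpoints the same scenario is named, and "measurements after this ICE will be imputed". Stops for any other reason follow a composite strategy: non-response for binary endpoints, return to baseline for continuous ones.

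SAP 5.1.5 gives the main rules. Under NRI, other-reason stoppers are "categorized as treatment failures after discontinuation". For commercial, supply and site-termination stoppers, "Participants with the ICE will be excluded from analysis for timepoints of interest after the ICE". The mBOCF text repeats that sentence. The justification in both places is: "The assumption behind this approach is that measurements after this ICE are missing completely at random".

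NRI is the main method for the co-primary endpoints (SAP 5.3.2), and ANCOVA with mBOCF is primary for continuous endpoints (SAP 5.1.5). Two other methods keep these participants in:

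- **mNRI**, for the co-primary and selected secondary endpoints: "missing data will be imputed using hybrid multiple imputation as a sensitivity analysis". SAP 5.3.3 adds that "an analysis in the PAS population using mNRI and observed case will also be presented as further analyses", and SAP 5.4.1.3 refers back to it for "sensitivity analyses that may be used for binary secondary endpoints".
- **MMRM**, for continuous endpoints, also as a sensitivity analysis (SAP 5.1.5, 5.4.1.3).

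SAP Appendix 2 does not list mNRI for PRO remission, PRO response, the CDAI remitter and non-remitter subsets, or the presence rows for extraintestinal manifestations, fistulae and resource use. Protocol 9.4.1.4 leaves the handling of switchers to the SAP.

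**The concern.** The two kinds of stop compete. A participant who has already stopped for lack of benefit or an adverse event can no longer switch to commercial drug, so that failure stays in the denominator for good. A participant who is doing well can still switch, and is then dropped. Exclusion therefore depends on the composite outcome being estimated, even when on-drug outcomes are unrelated to switching. The assumption cited in SAP 5.1.5 concerns post-event measurements and does not address this. For continuous endpoints there is also a plain conflict: SAP 1.1 imputes, SAP 5.1.5 excludes.

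Treatment lasts about 3 years or until commercial availability in the participant's country, whichever comes first (SAP 1.2; Protocol 1.1). Switching is thus part of the design and would fall mainly on the later visits that describe durability. The study makes no comparison and tests no hypothesis (Protocol 9.1; SAP 2), so point estimates with intervals are its main efficacy output. A Wilson interval around a mis-targeted rate does not show the problem.

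**Working it through.** The documents give no discontinuation, switching or on-drug response rates, so there is no planned figure to reproduce. The only planning number, 640 to 900 participants, does not enter.

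**Count example (assumed).** Of 100 participants, 20 stop early for other reasons, 40 of the remaining 80 later switch, and 80% of those on drug respond.

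- Target: 0.80 × 80 / 100 = 64.0%.
- SAP rule: 0.80 × 40 / (40 + 20) = 32/60 = 53.3%.

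**General form.** Let

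- S(t) = (1 − d)^(t/156), retention against other-reason stops, where d is the share stopping by Week 156;
- p = share of participants in countries where the drug becomes available, evenly over Weeks 52 to 156, and F(t) = (t − 52)/104;
- E(t) = p × (integral of S from 52 to t) / 104, the share excluded by t;
- r = on-drug response, and s = the response switchers would have had.

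Then:

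- SAP rule: N = r·S·(1 − pF) / (1 − E)
- SAP 1.1 target (switchers stay on drug to the visit): T1 = r·S·(1 − pF) + s·E
- Rate had there been no switching (switchers could still stop later for other reasons): T2 = r·S
- Error against SAP 1.1: N − T1 = E × (N − s)

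The error is zero only if nobody is excluded or s equals the reported rate. With s = r it also vanishes if there are no other-reason stops.

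**Base case (all assumed):** d = 20%, r = s = 80%, p = 50%. At Week 156, S = 0.80 and pF = 0.50. Mean S over Weeks 52 to 156 is 0.863, so E = 0.5 × 0.863 = 0.431. N = 0.32/0.569 = 56.3%. T1 = 0.32 + 0.8 × 0.431 = 66.5%. T2 = 64.0%.

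| Week | SAP rule | SAP 1.1 target | No switching |
|---|---|---|---|
| 52 | 74.3 | 74.3 | 74.3 |
| 76 | 71.0 | 71.9 | 71.8 |
| 100 | 67.3 | 69.9 | 69.3 |
| 124 | 63.1 | 68.2 | 67.0 |
| 156 | 56.3 | 66.5 | 64.0 |

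**Variations at Week 156**, in the same column order:

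| Change from base case | SAP rule | SAP 1.1 target | No switching |
|---|---|---|---|
| p = 10% | 63.0 | 64.5 | 64.0 |
| p = 25% | 61.2 | 65.3 | 64.0 |
| p = 75% | 45.3 | 67.8 | 64.0 |
| d = 10% | 67.4 | 73.3 | 72.0 |
| d = 30% | 46.3 | 59.6 | 56.0 |
| d = 10%, p = 10% | 71.5 | 72.3 | 72.0 |

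**Sign.** Against SAP 1.1 in the base case, the error is −10.2 points when s = 80%, −1.6 when s = 60%, zero when s = 56.3%, and +2.7 when s = 50%.

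**Continuous endpoints.** With s = r the ratios N/T1 = 0.846 and N/T2 = 0.879 do not depend on r, so they carry over to a mean change before covariate adjustment. For an assumed on-drug mean change of −150, mBOCF gives −105.5, against −124.7 (SAP 1.1) and −120.0 (no switching).

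**Does MMRM close the gap?** It was simulated with 1,000,000 participants, SD 70, within-person correlation 0.6, other-reason stops set to zero change and switchers missing. With the six CDAI visits (Weeks 12, 52, 76, 100, 124, 156) it gives about −115.7. With Weeks 52 and 156 only, as for endoscopy, it gives about −110.4. It narrows the gap without closing it.

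**The case against.** The strongest reply concerns size and reach.

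- **Co-primary endpoints.** They are read at Week 52, where the scenario above shows no bias, and nothing is tested. This stands: the point concerns later descriptive visits.
- **Magnitude.** The 10.2-point figure rests on assumed inputs and on the literal reading of SAP 1.1. Against the no-switching rate it is 7.7 points, and with 10% other-reason stops and 10% in availability countries it is below 1 point. Half of participants in such countries is not anchored in the documents. SAP version 1 dates from March 2020, before first patient visit, and the September 2024 protocol still lists EU use as outside the marketing authorization, so some early enrollees may have completed much of follow-up before any launch for Crohn's disease. This is inference, since no enrolment or launch dates are given, but the size is indeed unknown.
- **Existing mitigation.** The assumption is disclosed, and mNRI is listed for endoscopic response and for CDAI remission in the full primary analysis set. This stands, but those remain secondary results, and several binary rows lack them.
- **Direction.** For presence endpoints such as fistulae, the direction depends on how NRI codes failure. This also stands.
- **The remedy can miss too.** The SAP gives no imputation model. Drawing on-drug response only gives 66.5%, while allowing later other-reason stops gives 64.0%. In the base case 43% of participants would be imputed at Week 156.

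None of this removes the mismatch between the stated target and the main rule.

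**Conclusion.** The concern holds. The main NRI and mBOCF rules do not estimate the quantity SAP 1.1 defines once there are both commercial or supply stops before a visit and other-reason stops before those. Missing completely at random on-drug outcomes are not enough to rescue them. The logic is certain and follows from the rules themselves. The size is not: it could be about 1 point or, under the assumed base case, 10.2 points at Week 156 against SAP 1.1 (7.7 against no switching), and no upper bound can be set from the documents. The bias in response rates is downward when switching is independent of outcome, and reverses if switchers would have responded below the reported rate. Later visits up to Week 156 are exposed. It should be corrected before those visits are analysed.

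**What to change.** Revise SAP 1.1, 5.1.5 and Appendix 2:

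1. State the target: switchers remain on drug to the visit, or switchers could still stop later for other reasons.
2. For visits after a commercial, supply or site-termination stop, make multiple imputation of those participants the main binary analysis. Specify its model to match the target, including whether later other-reason stops are imputed. Keep NRI for other-reason stops and for sporadic missing data.
3. For continuous endpoints, impute these participants and return the others to baseline. This also aligns 5.1.5 with 1.1.
4. Apply the same rule to the PRO endpoints, the CDAI subsets and the presence rows.
5. Keep the current exclusion rule as a sensitivity analysis, report the number excluded per visit and group, and replace the missing-completely-at-random justification.

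If the no-switching target is chosen, inverse-probability-of-censoring weights, or exclusion by potential switch date whatever the earlier status, are alternatives. In a separate constant-hazard simulation (20% other-reason stops, 50% switching, 80% on-drug response) they gave 64.0% and 64.1% against a target of 64.0%, where the SAP rule gave 58.6%.

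The cost is a SAP revision and programming. The protocol's NRI rules stay intact, because Protocol 9.4.1.4 leaves switchers to the SAP. Imputation of switchers is already planned for binary endpoints but would be new work for continuous ones. The main late estimates would then rest on an imputation model that has still to be written.

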5.2 Participant Dispositions

[figure not shown]
The number of participants in the mITT/PAS population will be summarized for each originating study by Study AMAX intervention and by the intervention assigned in the originating study. Frequency counts and percentages of all participants who complete the study or who discontinue from the study intervention early will be presented. Reasons for early discontinuation of the study intervention or of the study will be listed and summarized by Study AMAX intervention and by the intervention assigned in the originating study.

5.3 Primary Endpoint(s) Analysis

5.3.1 Definition of Endpoint(s)

The co-primary endpoints are

Endoscopies performed up to a maximum of 14 days after the Week 52 visit date of Study AMAX, but before any additional dosing, will be used for the analysis of Week 52.

Descriptions and derivations of these endpoints are shown in Appendix 1 in Section 6.1. As described in Section 5.1.4, the proportions will be reported by the sequence of treatments in AMAM and AMAX.

5.3.2 Main Analytical Approach

Section 1.1 describes the primary estimand that will be used to assess the primary objective of this study.

All analyses presented will be descriptive using the PAS population and the methods described in Section 5.1.1 and Section 5.1.5. Specifically, the NRI method will be used based on a hybrid strategy for the intercurrent event of discontinuing treatment due to different reasons prior to time point of interest. Confidence intervals using the Wilson Score method will be presented. Additional details are described in Appendix 2 in Section 6.2.

5.3.3 Supplemental Analysis

In addition to the NRI imputation method, an analysis in the PAS population using mNRI and observed case will also be presented as further analyses (see Section 5.1.5) for binary endpoints. The co-primary endpoints will also be analyzed in the mITT population. Additional details are described in Appendix 2 in Section 6.2.

5.4 Secondary Endpoint(s) Analysis

5.4.1 Secondary Endpoint(s)

5.4.1.1 Definition of Endpoint(s)

Secondary endpoints are listed in Section 1.1 under Secondary.

Descriptions and derivations of these endpoints are shown in Appendix 1 in Section 6.1.

5.4.1.2 Main Analytical Approach

Section 1.1 describes the proposed estimands to assess secondary objectives of this study.

The main analytical approach for binary secondary endpoints may be done similarly as for the primary endpoints and is described in Section 5.3.2. The main analytical approach for continuous secondary endpoints from Study AMAM participants will utilize ANCOVA as described in Section 5.1.1. Details are described in Appendix 2 in Section 6.2.

5.4.1.3 Sensitivity Analysis

Refer to Section 5.3.3 for details regarding the methods used for sensitivity analyses that may be used for binary secondary endpoints. Additional details are described in Appendix 2 Section 6.2.

For continuous endpoints, MMRM will be used as sensitivity analysis (see Section 5.1.5).

5.5 Tertiary/Exploratory Endpoint(s) Analysis

Exploratory endpoints are listed in Section 1.1 under Tertiary/Exploratory.

Descriptions and derivations of exploratory endpoints as well as additional endpoints not specified in the protocol are shown in Appendix 1 in Section 6.1.

Additional endpoints and analyses not described in Appendix 1 in Section 6.1 or Appendix 2 in Section 6.2 will be described in supplemental analysis plans.

5.6 Safety Analyses

In general, safety evaluations will be based on the Safety Population for the Induction Period and Complete Study Period. Select safety analysis will also be performed for the continued access period as needed.

For the purpose of Study AMAX alone, the following are planned:

- Listing of Serious Adverse Events (SAEs)
- Listing of adverse events leading to permanent discontinuation of study drug
- Summary of SAEs (with different columns for the intervention groups specified in Section 5.1.4)
- Summary of AEs leading to permanent discontinuation of study drug (with different columns for the intervention groups specified in Section 4)

The safety data from this study will also be used as part of ongoing safety reviews. The safety data from this study will also be used as part of integrated summaries in submissions/disclosures and ongoing safety review through study end.

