5.1.3 Definition of Study Period Time Interval

The table below displays a list of study periods along with the definition of which participants will be considered to have entered the study period and when the individuals start and end the study period. The table shows both a date and a time.

To calculate the length of any time interval or time period in this study the following formula will be used:

 $Length\ of\ interval\ (days) = End\ Date - Interval\ Start\ Date + 1$

To convert any time length from days to years, the following formula will be used:

Length of interval (years) = Length of interval (days)/365.25

To convert any time length from days to weeks, the following formula will be used:

Length of interval (weeks) = Length of interval (days)/7

Only for the purpose of calculating the length of study period time intervals, the words "prior to" in the table below should be understood to mean "the day before" while the words "after" should be understood to mean "the day after." For the purpose of determining whether a date/time lies within an interval these words are intended to convey whether the start or end of the period is inclusive of the specified date.

Study Period	Interval Start Definition	Interval End Definition
Induction Period	At the date/time ^a of first dose of study intervention in Study AMAX. For participants who are assigned but not dosed, Induction Period starts on the date of study intervention assignment.	Prior to the start of Long-Term Extension Period. For participants who discontinue before or CCI visit, Induction Period ends at the latest date of study intervention discontinued date or last study intervention visit date.
Long-Term Extension Period	At the Week 12 dosing date/time ^a in Study AMAX. If the participant is unable to be dosed at the Week 12 visit, the Long-Term Extension Period starts at the Week 12 Visit. If the participant misses the Week 12 visit, the Long-Term Extension Period starts at Day 92.	After the CCI visit date. For participants who discontinue prior to CCI , Long-Term Extension Period ends at the latest date of study intervention disposition date or last study intervention visit date.
Follow-up Period	All participants who had Visit 801 or Visit 802 are considered to have entered the Follow-up Period. The latest of Induction Period or Long- Term Extension Period interval end date.	The last date of the last study visit and study disposition date.

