Complete Study Period	At the date/time ^a of first dose of study intervention. For participants who are assigned but not dosed, Complete Study Period starts on the date of study intervention assignment.	After the CCI visit date. For participants who discontinue prior to CCI, Complete Study Period ends at the latest date of study intervention disposition date or last study intervention visit date.

	At the date/time ^a of first dose of study intervention. For	
Complete Study Period +	participants who are assigned	The last date of the last study visit within
Continued Access Period	,	Continued Access Period.
	Period starts on the date of	
	study intervention assignment.	

Missing dose time will be imputed as the earliest time that is consistent with available data about dose time. For example, suppose the minutes are missing but hour is present. In this case, we would impute the minutes to be 0.

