5.1.4 Definition of Study Intervention by Study Period

The table below provides the study intervention groups to be displayed for each analysis population and analysis period.

Analysis	Analysis Period	Study Intervention Groups:
Population		
PAS/mITT/Safety population	Induction Period/Complete Study Period/ Continued Access Period	 AMAM miri/miri/ SC AMAM pBO/miri/ SC AMAM PBO/miri/ IV AMAM PBO/miri/ IV AMAM uste/uste/ SC AMAM uste/uste/ IV AMAM PBO/PBO/ SC AMAM PBO/PBO/ IV AII AMAM/ SC a All AMAM/ IV a All AMAM a All AMAM/ SC a Total a
PAS/mITT subset populations	Complete Study Period	PAS/mITT sub-population – Endoscopic Responder in the originating study: • AMAM miri/miri/ SC (co-primary analysis) • AMAM PBO/miri/ SC • AMAM uste/uste / SC • AMAM PBO/PBO/ SC • All AMAM SC a • Total a PAS/mITT sub-population – Endoscopic Nonresponder in the originating study: • AMAM miri/miri / IV • AMAM PBO/miri/ IV • AMAM uste/uste / IV • AMAM PBO/PBO/ IV • AMAM PBO/PBO/ IV • All AMAM IV a • Total a

Analysis Population	Analysis Period	Study Intervention Groups:		
		Other sub-population analysis:		
		 AMAM miri/miri/ SC AMAM miri/miri/ IV AMAM PBO/miri/ SC AMAM PBO/miri/ IV AMAM uste/uste/ SC AMAM uste/uste/ IV AMAM PBO/PBO/ SC AMAM PBO/PBO/ IV AII AMAM/ SC a All AMAM/ IV a All AMAM a All AMAM a Total a 		

Abbreviations: AMAG = Study I6T-MC-AMAG; AMAM = Study I6T-MC-AMAM; IV = intravenous; miri = mirikizumab; PBO = placebo; SC = subcutaneous; uste = ustekinumab; Q4W = every 4 weeks.

For endpoints utilizing the PAS/mITT subset populations, not all intervention groupings listed above may be shown.

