5.6.1 Extent of Exposure

Duration of exposure to study intervention will be summarized by study intervention group for the Safety Population. For the Complete Study Period, exposure will be calculated as (Date of end date of Complete Study Period – Date of start date of the Complete Study Period + 1 day) described in Section 5.1.3. Calculations will use the Safety Population in the Complete Study Period.

Total participant-years (PY) of exposure will be reported for the Safety Population by study intervention group in Section 4. Descriptive statistics will be provided for participants-weeks of exposure and the frequency of participants falling into different exposure ranges will be summarized.

- >0; ≥12 weeks; ≥36 weeks; ≥52 weeks; ≥68 weeks; ≥84 weeks; ≥100 weeks; ≥116 weeks; ≥140 weeks;
- >0 to <12 weeks; \geq 12 weeks to <36 weeks; \geq 36 weeks to <52 weeks; \geq 52 weeks to <68 weeks; \geq 68 weeks to <84 weeks; \geq 84 weeks to <100 weeks; \geq 100 weeks to <116 weeks; \geq 116 weeks to <140 weeks; \geq 140 weeks

Additional exposure ranges may be considered, if necessary. No p-values will be reported in these tables as they are intended to describe the study populations, rather than test hypotheses about them.

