5.6.2 Immunogenicity

Immunogenicity will be evaluated cumulatively, using data both from the participant's originating study and from the present study. Baseline for ADA assessment will be the baseline ADA assessment from the originating study, and postbaseline will be time after initiation of mirikizumab.

An individual sample is potentially examined multiple times in a hierarchical procedure to produce a sample anti-drug antibodies (ADA) assay result and potentially a sample neutralizing anti-drug antibodies (NAb) assay result. A participant has treatment-emergent anti-drug antibodies (TE-ADA) when ADA are induced or boosted by exposure to study drug; i.e., when at least one postbaseline ADA sample has a 4-fold increase in titer, compared to baseline (if ADA were present at baseline) or has a titer 2-fold greater than the minimum required dilution of 1:10 (if no ADA were present at baseline).

Compound level safety standards will be followed in the analyses of immunogenicity. The summary of TE ADA positive (TE ADA+), TE ADA+ by titers and TE ADA+ with neutralizing antibody (NAb) status to mirikizumab will be produced for the mITT population (including originating studies and Study AMAX).

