6.6 Appendix 6: Clinical Trial Registry Analyses

Additional analyses will be performed for the purpose of fulfilling the Clinical Trial Registry (CTR) requirements.

Analyses provided for the CTR requirements include the following:

Summary of adverse events (AEs), provided as a dataset which will be converted to an XML file. Both serious adverse events (SAEs) and 'Other' AEs are summarized by study intervention group, by MedDRA PT.

- An AE is considered 'Serious' whether or not it is a TEAE.
- An AE is considered in the 'Other' category if it is both a TEAE and is not serious. For each SAE and 'Other' AE, for each term and study intervention group, the following are provided:
 - o the number of participants at risk of an event
 - o the number of participants who experienced each event term
 - o the number of events experienced.
- Consistent with www.ClinicalTrials.gov requirements, 'Other' AEs that occur in fewer than 5% of participants/subjects in every study intervention group may not be included if a 5% threshold is chosen (5% is the minimum threshold).
- Adverse event reporting is consistent with other document disclosures (e.g., the CSR, manuscripts, and so forth.

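### By default, the AMAX-only SAE summary by group stops at the end of treatment and leaves out SAEs that start in post-treatment follow-up

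*SAP*

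**What the plan says.** SAP 5.6 gives a general rule for safety outputs: "In general, safety evaluations will be based on the Safety Population for the Induction Period and Complete Study Period". The only other period it names is continued access, for selected analyses as needed. It then lists the AMAX-only outputs. One is a summary of SAEs by the intervention groups of SAP 5.1.4, and that bullet names no period.

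SAP 5.1.3 defines the periods. For a participant who stops early, "Complete Study Period ends at the latest date of study intervention disposition date or last study intervention visit date". The Follow-up Period is separate: it opens when the Induction or Long-Term Extension Period closes and runs to the last study visit or study disposition. Entry is defined by attendance: "All participants who had Visit 801 or Visit 802 are considered to have entered the Follow-up Period".

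For the full PAS, mITT and safety populations, SAP 5.1.4 gives display groups for "Induction Period/Complete Study Period/ Continued Access Period". SAP 5.6.1 says of exposure: "Calculations will use the Safety Population in the Complete Study Period".

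**The concern.** The name Complete Study Period suggests the whole study, but the definition covers treatment only. A programmer who follows the 5.6 default will build the SAE summary on that period and drop every SAE whose onset falls in follow-up.

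Three things make this more than a matter of labelling.

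- **The events are collected.** Participants who stop drug early are to attend Visits 801 and 802 (Protocol 7.1 and 7.1.2). Adverse events are scheduled at both (Protocol Table AMAX.1-3), and every adverse event after the first AMAX dose is recorded (Protocol 8.3.2).
- **The protocol sets no such limit.** Protocol 9.4.4 plans an SAE listing and summary for the AMAX report without restricting the period, and SAP Appendix 3 declares no change from the protocol.
- **Two tables can disagree.** The registry table in SAP 6.6 counts SAEs by group whether or not they are treatment-emergent and gives no period limit. The same section says "Adverse event reporting is consistent with other document disclosures", with the CSR as an example.

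At stake is the by-group SAE count that a reader of the AMAX report will take as the count for the study.

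**Working it through.** The plan gives no figure on this point to reproduce. The check compares the period boundaries with the outputs, then sizes the window.

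**1. Where the periods end (SAP 5.1.3)**

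| Period | Early discontinuer | Completer |
|---|---|---|
| Long-Term Extension | "Long-Term Extension Period ends at the latest date of study intervention disposition date or last study intervention visit date" | After a redacted visit |
| Complete Study | "Complete Study Period ends at the latest date of study intervention disposition date or last study intervention visit date" | After a redacted visit |
| Follow-up | Starts at the end of Induction or Long-Term Extension; ends at last study visit or study disposition | Same rule |

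For early discontinuers the first two rows use the same closing rule, so the Complete Study Period ends where follow-up begins. For completers the closing visit is redacted in both rows. The matching wording implies that the two periods also close together there, but that is an inference.

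**2. Which outputs use the Follow-up Period**

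| Place | Period used | Follow-up named? |
|---|---|---|
| SAP 5.1.4, display groups | Induction, Complete Study, Continued Access | No |
| SAP 5.6, SAE summary | None of its own, so the default applies | No |
| SAP 5.6.1, exposure | Complete Study | No |
| SAP 5.6.2, immunogenicity | Window given in words: "postbaseline will be time after initiation of mirikizumab" | Not by name, but the wording admits follow-up samples |

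SAP 5.1.3 also defines a combined Complete Study plus Continued Access Period. It has no equivalent that adds follow-up.

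**3. Size of the window**

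Inputs: follow-up f = 12 to 16 weeks (Protocol 4.1, SAP 1.2) and treated time t at cut points taken from SAP 5.6.1. Week 156 is added for completers.

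Share of observed time lying in follow-up = f / (t + f)

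| Treated weeks t | f = 12 | f = 16 |
|---|---|---|
| 12 | 12/24 = 50.0% | 16/28 = 57.1% |
| 52 | 12/64 = 18.8% | 16/68 = 23.5% |
| 100 | 12/112 = 10.7% | 16/116 = 13.8% |
| 140 | 12/152 = 7.9% | 16/156 = 10.3% |
| 156 (completer, inferred) | 12/168 = 7.1% | 16/172 = 9.3% |

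As an upper bound in person-years, suppose all of the expected 640 to 900 participants entered a 12- to 16-week follow-up: 640 × 12 × 7 / 365.25 = 147.2, and 900 × 16 × 7 / 365.25 = 276.0. The true figure will be lower, because participants who move into continued access skip Visits 801 and 802.

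These are shares of person-time, not of SAEs. The documents give neither a discontinuation rate nor an SAE rate for follow-up.

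**The case against.** The strongest reply is that nothing in SAP 5.6 excludes follow-up SAEs. The rule opens with a general qualifier, the SAE summary bullet names no period, and the table specifications, where a period would normally be fixed, are in a separate document that was not available. Protocol 9.4.4 and SAP 6.6 can be read as supporting an unrestricted summary. This stands in part: the omission follows from a default and is not an express exclusion. But the default is the only period rule that 5.6 offers for this table, and two programmers could reasonably produce different counts from it.

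Second, the completer case rests on redacted text. That stands, and the redaction is no fault of the plan. The rule for early discontinuers is legible and carries the point alone.

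Third, little is lost. The registry table and the integrated summaries state no such limit. The SAE listing names no period either, and a listing ordinarily shows every recorded event. This is correct and limits the consequence to one table. A listing, however, does not give counts by group, and the SAE summary is the by-group SAE count planned in 5.6.

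Fourth, an on-treatment table that matches the exposure in 5.6.1 is coherent, and follow-up events may arise under other drugs, because Protocol 10.7 allows otherwise prohibited medication once study drug has stopped and the early termination visit is done. That is a good reason to show the two windows apart, not to leave one out.

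**Conclusion.** The concern holds. Under the stated default, the AMAX-only SAE summary by group omits SAEs, deaths included, with onset after treatment ends, although they are collected and the protocol plans the summary without that limit. The SAP should be changed on this point, but the effect is confined to this one summary, and the integrated safety assessments are not affected.

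The omitted window ranges from about half of observed time for someone who stops at Week 12 to about a tenth for someone who stops at Week 140. How many SAEs that represents is unknown. The conclusion assumes that the 5.6 default governs the SAE summary and that the unseen table specifications do not override it. For completers it also assumes that the redacted closing visit follows the Long-Term Extension wording. A disposition date later than the last treatment visit would shorten the omitted window.

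**What to change.** In SAP 5.6, state that the SAE summary, deaths included, runs from the first AMAX dose to the end of the Follow-up Period, with on-treatment and follow-up counts in separate columns. On-treatment counts then still match the exposure in 5.6.1, and events that may have arisen under other therapy stay apart. Add the Follow-up Period to the analysis periods in 5.1.4.

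Tie the end of the window to last study visit or study disposition, not to attendance. As 5.1.3 stands, a participant who dies after the early termination visit but before Visit 801 never enters the Follow-up Period.

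The cost is a sentence, an entry in 5.1.4 and a table column. No new data are needed. The SAE count may rise slightly.
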